10.9.6. Substudy A Design

10.9.6.1. Overall Design

This study is designed to evaluate the safety, tolerability, and immunogenicity of RSVpreF and a modified RNA vaccine (qIRV) against RSV and influenza when administered as a combined vaccine and when administered alone. This 3-visit study will initially be conducted as a Phase 1b, single-site, parallel-group, randomized, placebo-controlled, observer-blinded substudy.

Approximately 250 healthy participants (n=125 per group) will be enrolled in Substudy A. Note: "Enrolled" means a participant's agreement to participate in a clinical study following completion of the informed consent process.

Healthy adults ≥60 years of age will be randomized 1:1 to either:

- Group 1: combination (RSVpreF + qIRV) (Visit A101) followed by placebo (Visit A102) or
- Group 2: sequential administration of qIRV (Visit A101) followed by RSVpreF (Visit A102) administered 1 month apart.

Randomization will be stratified by 3 age groups (60-64, 65-79, and ≥80 years) within each study site. To ensure a broad representation of age groups (participants at least 65 years of age) for the current recommendation on seasonal influenza vaccination, no more than 40 participants 60 through 64 years of age will be vaccinated.

Blood will be collected prior to each vaccination and at the final study visit.

Local reactions and systemic events occurring within 7 days after each vaccination will be recorded in an e-diary device or smartphone app.

AEs and SAEs will be collected from the signing of informed consent through study completion.

This study will have stopping rules that will apply to participants as specified in Section 8.3.6 with monitoring by designated unblinded sponsor site staff on an ongoing basis. If a stopping rule is confirmed as having been met, further randomization and administration of Vaccination 1 will be paused while additional information is gathered, and cumulative unblinded safety data will be reviewed by the IRC. Participants who have received Vaccination 1 will continue further study visits and procedures as scheduled. A charter for the IRC will be prepared and finalized before the first participant provides informed consent.

The IRC will review cumulative safety data from at least 10 participants who have received RSVpreF + qIRV. Concurrently, enrollment will pause until the IRC confirms a satisfactory safety assessment, whereupon enrollment will recommence.

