2.3. Study Design

2.3.1. Substudy A

This is a Phase 1b, parallel-group, randomized, placebo-controlled, observer-blinded substudy. Approximately 250 healthy adults ≥ 60 years of age will be randomized 1:1 to either:

- Group 1: combination (RSVpreF + qIRV) (Visit A101) followed by placebo (Visit A102) or
- Group 2: sequential administration of qIRV (Visit A101) followed by RSVpreF (Visit A102) administered 1 month apart.

Randomization will be stratified by 3 age groups (60 to 64, 65 to 79, and \geq 80 years) within each study site. There are 3 scheduled study visits each 1 month apart. To assess immunogenicity, blood samples will be collected prior to vaccination at Visit A101 (Day 1) and Visit A102 (Month 1), and at Visit A103 (Month 2).

Local reactions (redness, swelling, and pain at the injection site) and systemic events (fever, headache, fatigue, nausea, vomiting, diarrhea, chills, new or worsened muscle pain, and new or worsened joint pain) occurring within 7 days after each vaccination visit (Visit A101 and Visit A102) will be recorded in an e-diary device or smartphone app.

AEs and SAEs will be collected from the signing of the informed consent through Visit A103.

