3. ENDPOINTS AND BASELINE VARIABLES: DEFINITIONS AND CONVENTIONS

3.1. SSA Primary Endpoint(s)

3.1.1. Primary RSV Immunogenicity Endpoints

RSV A– and RSV B–neutralizing antibody titers will be determined on sera collected at all 3 visits. Only the RSV NTs measured at the Month 1 visit in the combination (RSVpreF + qIRV) group, and RSV NTs measured at the Month 2 visit for the sequential-administration group, are relevant to the primary RSV immunogenicity endpoints.

Titers above the LLOQ are considered accurate and their quantitated values will be reported. Refer to Section 5.3.2 for LLOQ details. Titers below the corresponding LLOQ, or denoted as BLQ, will be set to $0.5 \times$ LLOQ for analysis. Missing assay results will not be imputed.

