3.1.2. Primary HAI Immunogenicity Endpoints

HAI titers to the influenza strains will be determined on sera collected at the first 2 visits, but only the immunogenicity results for HAI measured in the combination (RSVpreF + qIRV) group, and in the sequential-administration qIRV group at the Month 1 visit, are relevant to the primary HAI immunogenicity endpoints.

Titers above the LLOQ are considered accurate and their quantitated values will be reported. Refer to Section 5.3.2 for LLOQ details. Titers below the corresponding LLOQ, or denoted as BLQ, will be set to $0.5 \times$ LLOQ for analysis. Missing assay results will not be imputed.

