3.3. SSB Secondary Endpoint(s)

3.3.1. SSB Secondary RSV Immunogenicity Endpoints

RSV A– and RSV B–neutralizing antibody titers will be determined on sera collected at all 2 visits. The RSV NTs measured at the Month 1 visit after vaccination in both combination groups are relevant to the secondary RSV immunogenicity endpoints.

Titers above the LLOQ are considered accurate and their quantitated values will be reported. Refer to Section 5.3.2 for LLOQ details. Titers below the corresponding LLOQ, or denoted as BLQ, will be set to $0.5 \times$ LLOQ for analysis. Missing assay results will not be imputed.

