3.6. Safety Endpoints

3.6.1. Adverse Events

Guillain-Barre syndrome (from Day 1 through Day 43 after vaccination with RSVpreF or (RSVpreF+qIRV), where Day 1 is the day of vaccination), atrial fibrillation (from vaccination with RSVpreF or (RSVpreF+qIRV) through the Month 1 visit), and polyneuropathy (from Day 1 through Day 43 after vaccination with RSVpreF or (RSVpreF+qIRV), where Day 1 is the day of vaccination) have been identified as Tier 1 events for RSVpreF. The RSV program list of Tier 1 MedDRA PTs, maintained by the safety risk lead, is in the CAETeLiSt and is referenced in the safety surveillance review plan for the program. The current list of Tier 1 events should be confirmed to ensure that appropriate Tier 1 events will be used to produce final tables/graphs before conducting an analysis. Because RSVpreF is a vaccine component of the combination vaccine and is also study vaccine, these Tier 1 events are defined in this study.

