6.5. Safety Summaries and Analyses

6.5.1. Adverse Events

For both SSA and SSB: For all of the AEs categorized in Section 3.1.3.3 and Section 3.1.3.4, each individual AE including SAE after vaccination will be categorized by the MedDRA PT and descriptively summarized with count, percentage, and 95% CI for vaccine group.

For Tier 1 events, the 2-sided 95% CIs for the difference in the percentage of participants reporting the events between the RSVpreF contained group and the control group will be calculated using the test statistic proposed by Miettinen and Nurminen³; in addition, the asymptotic p-values will also be presented for the difference in the percentage of participants reporting the events, based on the same test statistic and under the assumption that the test statistic is asymptotically normally distributed.

Because all participants enrolled in this study are expected to receive either RSVpreF or (RSVpreF+qIRV), there is no control in this study. Therefore, the intervention group will be all participants who received (RSVpreF+qIRV) or RSVpreF from both SSA and SSB, and the control group will be from RSVpreF pivotal Phase 3 study (C3671013) who received placebo only. The count for each Tier 1 event and denominator from C3671013 placebo group will be provided in this Tier 1 AE analysis.

It should be recognized that most studies are not designed to reliably demonstrate a causal relationship between the use of a pharmaceutical product and an AE or a group of AEs. Except for selecting events in unique situations, studies do not employ formal adjudication procedures for the purpose of event classification. As such, safety analysis is generally considered an exploratory analysis and its purpose is to generate hypotheses for further investigation.

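### The Tier 1 atrial fibrillation window closes at the Month 1 visit, which by the SAP's own Substudy A labels is the visit at which the sequential group receives RSVpreF

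*SAP*

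**What the plan says.** SAP Section 3.6.1 lists three Tier 1 events. Guillain-Barre syndrome and polyneuropathy have windows counted in days from vaccination. The third is "atrial fibrillation (from vaccination with RSVpreF or (RSVpreF+qIRV) through the Month 1 visit", with no visit number and no statement of which dose the month is counted from.

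For Substudy A the SAP fixes the labels in Section 2.3.1: "Visit A102 (Month 1), and at Visit A103 (Month 2". The same section describes Group 2 as "sequential administration of qIRV (Visit A101) followed by RSVpreF (Visit A102) administered 1 month apart".

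Two endpoint definitions apply these labels to Group 2. Section 3.1.1 takes "RSV NTs measured at the Month 2 visit for the sequential-administration group", which is the visit 1 month after RSVpreF. Section 3.1.2 takes HAI results "in the sequential-administration qIRV group at the Month 1 visit", which is A102, 1 month after qIRV.

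For the Tier 1 comparison, Section 6.5.1 states that "the intervention group will be all participants who received (RSVpreF+qIRV) or RSVpreF from both SSA and SSB". The comparator is the placebo group of the pivotal RSVpreF Phase 3 study. The outputs are a 95% CI for the difference in percentages and a p-value.

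**The concern.** Once the labels are fixed as calendar visits, the Month 1 visit for Group 2 is the visit at which RSVpreF is injected. A window that starts at that injection and ends at that visit contains only the part of the visit after the dose. Atrial fibrillation arising between A102 and A103 would not count as a Tier 1 event for this group, but its members would still be in the denominator.

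The other groups are not affected. The combination group of Substudy A is vaccinated at A101 and has its Month 1 visit at A102. Substudy B participants are vaccinated at B101 and seen at B102.

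At stake is a safety percentage compared formally with an external placebo group. People counted with almost no time at risk pull that percentage down, so the error favours a finding of no difference.

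**Working it through.** **1. Which visit the label selects**

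| Group | RSVpreF-containing dose | Visit labelled Month 1 | Visit 1 month after that dose |
|---|---|---|---|
| Substudy A Group 1 (combination) | A101 | A102 | A102 |
| Substudy A Group 2 (sequential) | A102 | A102 | A103 |
| Substudy B, both groups | B101 | B102 | B102 |

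The last two columns differ only for Group 2.

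**2. How many people this concerns**

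The planned sizes come from Protocol Section 10.9.6.1, "Approximately 250 healthy participants (n=125 per group) will be enrolled in Substudy A", and Section 10.10.6.1 (about 200, 100 per group). They are consistent: 2 × 125 = 250 and 2 × 100 = 200. Neither document states the pooled Tier 1 total. It follows by addition:

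- all recipients of an RSVpreF-containing dose: 125 + 125 + 200 = 450
- Group 2 share: 125/450 = 27.8%
- recipients with a full window under the literal label: 450 − 125 = 325

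**3. Effect on the percentage, if the label is applied literally**

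Let p be the 1-month risk, equal across groups. Events are counted in 325 people and divided by 450:

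- observed percentage = 325p/450 = 0.722p, an understatement of 27.8%

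**4. Effect on the upper limit with no events**

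The exact (Clopper-Pearson) two-sided 95% upper limit for 0 events in N is 1 − 0.025^(1/N).

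- N = 450: 0.82%
- N = 325: 1.13%

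The full denominator makes the limit look tighter than the followed-up participants support.

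**5. Effect on the chance of seeing any event**

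The documents give no atrial fibrillation rate, so the risks below are assumptions. P(at least 1) = 1 − (1 − p)^N, and the shift in the observed percentage is 0.278p.

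| Assumed 1-month risk | Expected events, 450 followed | Expected events, 325 followed | P(≥1), 450 | P(≥1), 325 | Shift (percentage points) |
|---|---|---|---|---|---|
| 0.1% | 0.45 | 0.33 | 36% | 28% | 0.03 |
| 0.2% | 0.90 | 0.65 | 59% | 48% | 0.06 |
| 0.5% | 2.25 | 1.63 | 90% | 80% | 0.14 |

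**The case against.** The best reply is that the label is meant relative to the dose. The window starts at vaccination with the RSVpreF-containing product, so its end would naturally be 1 month after that dose, which is A103 for Group 2. The SAP does use the label this way for Substudy B: Section 3.3.1 refers to "The RSV NTs measured at the Month 1 visit after vaccination in both combination groups". The safety endpoint table in Section 3.1.3 takes AEs after RSVpreF alone from Vaccination 2 to the end of the study, which is A102 to A103. A window that closes at the dosing visit serves no purpose, and a programmer might well query it.

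Much of this stands, and A103 is probably what was intended. But Section 3.6.1 does not say so. It lacks the words after vaccination that Section 3.3.1 includes. The Section 3.1.3 table governs a different endpoint, and Tier 1 windows are set separately. Sections 2.3.1, 3.1.1 and 3.1.2 all point a programmer to A102. Section 3.6.1 also asks that the Tier 1 list be confirmed before analysis, but that concerns which events are on the list and does not settle the window.

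A reader might infer more than the documents support:

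- **That Group 2 has no safety follow-up after RSVpreF.** It has. SAP Section 2.3.1 collects AEs and SAEs through A103, which the protocol schedules 28 to 35 days after Vaccination 2. Atrial fibrillation in that interval would still appear in the AE summaries by preferred term and vaccine group, and in the SAE summaries if serious.
- **That the SAP settles on a zero-length window.** It does not. The wording can be read two ways, and even the literal reading includes the time after the dose at A102.
- **That the planned output would show a true ratio of 1.0 as 0.72.** The planned measure is a difference in percentages. The 0.72 factor applies to the intervention percentage alone.

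The likely absolute effect is also small, as step 5 of the working shows, and Section 6.5.1 describes safety analysis as generally exploratory.

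**Conclusion.** The rule is wrong as written. It conflicts with the SAP's own Substudy A visit labels for one of the groups it covers, even though the intended end of the window is probably A103.

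The reach is narrow: one row of the pooled Tier 1 table. The Guillain-Barre and polyneuropathy windows do not use the visit label and are not affected by it.

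If the label is programmed literally, about 27.8% of the planned denominator contributes essentially no time at risk, and the atrial fibrillation percentage is about 0.72 of its true value. If A103 is programmed, there is no bias. The size rests on these assumptions:

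- Planned enrolment is met and every Group 2 participant receives RSVpreF. The figures 125 and 450 are approximate, and anyone who leaves before A102 never enters the denominator.
- The 1-month risk is equal across groups.
- The external placebo count covers a full month. The SAP does not state the window for that count.

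The direction, toward missing a signal, is the reason to correct the sentence before the analysis is run.

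**What to change.** In SAP Section 3.6.1, replace the end of the atrial fibrillation window with: through the visit 1 month after the RSVpreF-containing dose (A102 for Substudy A Group 1, A103 for Substudy A Group 2, B102 for Substudy B).

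This costs one sentence in the SAP. It needs no new data, because AEs are already collected through A103, and it changes no study procedure. If A103 was always intended, the edit only confirms the plan. With it, all 450 planned recipients have a scheduled window of 28 to 35 days.

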3.6.2. Vital Sign Data

For both Substudy A and Substudy B, the temperature collected at baseline will only be used to assess any potential protocol deviation for a vaccination temporary delay. Therefore, it will not be included as a baseline variable. Only blood pressure and pulse rate will be included as a baseline vital-sign variable.

3.6.3. Myocarditis or Pericarditis

Any study participant who reports acute chest pain, shortness of breath, palpitations, or any other symptom(s) that might be indicative of myocarditis or pericarditis within 28 days after Vaccination 1 must be specifically evaluated for possible myocarditis or pericarditis. ECG and measurement of troponin will be performed locally for potential myocarditis/pericarditis evaluation. These events will also be entered as AEs, which will link with signs and symptoms of potential cardiac disease by AE ID in the CRF. The AE verbatim term will be entered/modified in the CRF based on reviews/evaluations of various tests, according to the CRF completion guideline.

The variables in the table below will be derived for these assessments, and the derivation will be based on the AE verbatim term according to Tejtel¹:

Brighton Collaboration case definition	Protocol	Derivation
and level of diagnostic certainty		
Level 1 definitive myocarditis	Confirmed myocarditis	AE verbatim=confirmed myocarditis
Level 1 definitive pericarditis	Confirmed pericarditis	AE verbatim=confirmed pericarditis
Level 2 probable myocarditis	Suspected or probable myocarditis	AE verbatim=suspected or Probable myocarditis
Level 2 probable pericarditis	Suspected or probable pericarditis	AE verbatim=suspected or Probable pericarditis
Level 3 possible myocarditis	Possible myocarditis	AE verbatim=possible myocarditis
Level 3 possible pericarditis	Possible pericarditis	AE verbatim=possible pericarditis

DMB02-GSOP-RF02 7.0 Statistical Analysis Plan Template 31-Jan-2022 PFIZER CONFIDENTIAL TMF Doc ID: 98.03 Page 31 of 46

Brighton Collaboration case definition and level of diagnostic certainty	Protocol	Derivation
N/A	Potential myocarditis or pericarditis only	AE verbatim not in any of above 6 but with a nonmissing signs and symptoms page with symptom onset within 28 days after Vaccination 1

4. ANALYSIS SETS (POPULATIONS FOR ANALYSIS)

Data for all participants will be assessed to determine if participants meet the criteria for inclusion in each analysis population prior to unblinding and releasing the database, and classifications will be documented per standard operating procedures.

Substudy A:

Participant Analysis Set	Description
Enrolled	All participants who have a signed ICD.
Randomized population	All enrolled participants who are assigned a randomization number in the IRT system.
Safety population	All enrolled participants who receive the study intervention either in combination RSVpreF + qIRV, or as placebo, qIRV, or RSVpreF alone.
E-diary safety population	All enrolled participants who receive the study intervention either in combination RSVpreF + qIRV, or as placebo, qIRV, or RSVpreF alone, and having at least 1 day of e-diary data transferred.

Major protocol violations will be determined by clinical review. A major protocol violation is a protocol violation that, in the opinion of the sponsor's study medical monitor, would materially affect assessment of immunogenicity or efficacy, eg, participant receipt of a prohibited vaccine or medication/treatment that might affect immune response, or a medication error with suspected decrease in potency of the vaccine. The sponsor's medical monitor will identify those participants with protocol violations before any analysis is carried out.

Substudy A:

Defined Analysis Set	Description	
Evaluable RSV immunogenicity population	Description All participants who meet the following criteria: Are eligible for the study. Receive the study intervention(s) to which they were randomized (RSVpreF + qIRV at Visit A101 for the combination group, and RSVpreF at Visit A102 for the sequential-administration group). Have the 1-month postvaccination blood collection within 27 to 42 days afte vaccination (Visits A102 to A101 for the combination group and Visits A10 to A102 for the sequential-administration group). Have at least 1 valid and determinate RSV NT result at the 1-month postvaccination blood collection.	
	CSOD DE02 7.0 Statistical Analysis Plan Tomplate 21 Jan 2022	

DMB02-GSOP-RF02 7.0 Statistical Analysis Plan Template 31-Jan-2022 PFIZER CONFIDENTIAL

TMF Doc ID: 98.03

Page 32 of 46

Defined Analysis Set	Description		
	Have no major protocol violations from randomization through the 1-month postvaccination blood collection.		
Evaluable HAI immunogenicity population	 All participants who meet the following criteria: Are eligible for the study. Receive the study intervention(s) to which they were randomized at Visit A101 (RSVpreF + qIRV in the combination group versus qIRV in the sequential-administration group). Have the 1-month postvaccination blood collection for HAI assay within 27 to 42 days after vaccination (Visits A102 to A101). Have at least 1 valid and determinate HAI result at the 1-month postvaccination blood collection. Have no major protocol violations from randomization through the 1-month postvaccination blood collection (through Visit A102). 		
mITT immunogenicity population	All participants who were randomized and had at least 1 valid and determinate assay result at any time point after receiving study intervention (combination RSVpreF + qIRV, placebo, qIRV alone, or RSVpreF alone).		

Like SSA, SSB analysis sets are descripted as following:

Substudy B:

Participant Analysis Set	Description	
Enrolled	All participants who have a signed ICD.	
Randomized population	All enrolled participants who are assigned a randomization number in the IRT system.	
Safety population	All enrolled participants who receive the study intervention (0.5 mL or 1.0 mL).	
E-diary safety population	All enrolled participants who receive the study intervention (0.5 mL or 1.0 mL) and with at least 1 day of e-diary data transferred.	
Evaluable immunogenicity population	 All participants who meet the following criteria: Are eligible for the study. Receive the study intervention to which they were randomized at Visit B101. Have the 1-month postvaccination blood collection for serology assay testing within an appropriate window. Have at least 1 valid and determinate assay result at the 1-month postvaccination blood collection. Have no major protocol violations from randomization through the 1-month postvaccination blood collection (through Visit B102). 	
mITT immunogenicity population	n All participants who are randomized and have at least 1 valid and determinate assay result after receiving study intervention.	

If a participant received study intervention not as randomized, the safety analysis set will be based on the vaccine group actually received and the immunogenicity analysis set will be based on the vaccine group as randomized.

5. GENERAL METHODOLOGY AND CONVENTIONS

5.1. Hypotheses and Decision Rules

There is no statistical hypothesis in Substudy A and Substudy B.

The estimands corresponding to each primary, secondary, or exploratory objective are described in Section 2.2.

5.2. General Methods

Unless otherwise stated, "CI" refers to a 2-sided CI in this document for 95% CI.

Descriptive statistics for binary variables are the proportion (%) and the numerator (n) and the denominator (N) used in the proportion calculation. The 95% CI for percentage, and for the difference in percentages, may also be presented where appropriate.

Unless otherwise specified, descriptive statistics for continuous variables are n, mean, median, standard deviation, minimum, and maximum.

The subsections below describe the analysis for different types of endpoints.

